2.4.4.2 Analyses of key secondary efficacy endpoints

Statistical analysis methods for the key secondary endpoints are presented below.

2.4.4.2.1 Change from baseline in percentage predicted pre-bronchodilator (pre-BD) FEV₁ at Week 12

Primary statistical model and adjustment for covariates

The analysis of change from baseline in % predicted pre-BD FEV₁ at Week 12 is to assess the efficacy of dupilumab regardless of treatment adherence. The absolute change from baseline in % predicted FEV₁ at Week 12 will be analyzed using a mixed-effect model with repeated measures (MMRM) approach. The analysis for change from baseline in % predicted pre-BD FEV₁ will be performed in the Type 2 inflammatory asthma phenotype, baseline blood eosinophils ≥ 0.3 Giga/L, baseline blood eosinophils ≥ 0.15 Giga/L, baseline FeNO ≥ 20 ppb and full ITT populations.

When performing the key secondary endpoint analysis in the Type 2 inflammatory asthma phenotype, baseline blood eosinophils ≥ 0.15 Giga/L, and full ITT populations, the model will include change from baseline in % predicted FEV₁ values up to Week 12 as response variables, and treatment, baseline weight, region, ethnicity, baseline eosinophil level, baseline FeNO level, baseline ICS dose level, visit, treatment by-visit interaction, baseline % predicted FEV₁ value and baseline-by-visit interaction as covariates. When performing the key secondary endpoint analysis in the baseline blood eosinophils ≥ 0.3 Giga/L population, the baseline eosinophil level will be removed from the model covariates. When performing the key secondary endpoint analysis in the baseline FeNO ≥ 20 ppb population, the baseline FeNO level will be removed from the model covariates.

Treatment group, baseline weight, region, baseline eosinophil level, baseline FeNO level, ethnicity, baseline ICS dose level, and visit will be treated as categorical variables. For patients who discontinue the treatment before Week 12, they will be asked and encouraged to return to the clinic for all remaining study visit and the additional off-treatment % predicted FEV₁ values measured up to Week 12 will be included in the primary analysis. For patients who withdraw from the study before Week 12, % predicted FEV₁ values will be missing after study discontinuation. No imputation will be performed for missing values in the primary analysis. This estimand

compares the change from baseline in % predicted pre-BD FEV1 for the patients randomized to the dupilumab and placebo arms, regardless of what treatment patients actually received. It assesses the benefits of the treatment policy or strategy relative to placebo.

An unstructured correlation matrix will be used to model the within-patient errors. Parameters will be estimated using restricted maximum likelihood method with the Newton-Raphson algorithm. Statistical inferences on treatment comparisons for the change from baseline in % predicted FEV1 at Week 12 will be derived from the mixed-effect model. Difference in LS mean change from baseline, the corresponding 95% CI and the p-value with Kenward-Roger adjustment will be provided for comparison for dupilumab against placebo. In addition, descriptive statistics including number of patients, mean, standard error and LS mean of change from baseline will be provided.

A sample SAS code can be found below:

```
proc mixed data=adsd.adre method=reml;

    where paramcd='FEV1PP' and ATPT='PRE-BRONCHODILATOR' and avisitn ge 3 and
    avisitn le 8 and ittfl='Y';

    class subjid weight eosblgpn1 fenoblgn1 ics trt01pn avisitn cntygr1n ethnicity;

    model chg = trt01pn weight ics eosblgpn1 fenoblgn1 cntygr1n ethnicity avisitn
    trt01pn*avisitn base base*avisitn/ddfm=kr residual;

    repeated avisitn/type=un subject=subjid;

    lsmeans trt01pn*avisitn /pdiff cl;

    estimate 'dupilumab vs Placebo at Week 12 Visit 8'

    trt01pn -1 1 trt01pn*avisitn 0 0 0 0 0 -1 0 0 0 0 0 1/cl;

run;
```

The primary estimand for the key secondary endpoint is summarized as in below [Table 7](#).

Table 7 - Summary of primary estimand for key secondary endpoint

Endpoint Category (estimand)	Estimands			
	Endpoint	Population	Intercurrent event(s) strategy and missing data handling	Population-level summary
Primary objective: The primary objective is to evaluate the efficacy of dupilumab in children 6 to <12 years of age with uncontrolled persistent asthma				
Key secondary endpoint (treatment policy)	Change from baseline in pre-bronchodilator % predicted forced expiratory volume in 1 second (FEV1) at Week 12	Type 2 inflammation phenotype; Patients with baseline blood eosinophils \geq 0.3 Giga/L population	The intercurrent events will be handled as follows: Discontinuation of study Treatment before Week 12: Off-study treatment data up to Week 12 will be included in the analysis (treatment policy strategy). In addition, the missing data imputation rules are as follows: In addition, missing data will be imputed latently by MMRM based on missing at random assumption	In patients with Type 2 inflammatory asthma phenotype, the key secondary endpoint will be analyzed using MMRM with change from baseline in % predicted FEV1 values up to Week 12 as response variable, and treatment, age, baseline weight, region, sex, ethnicity, baseline height, baseline eosinophil level, baseline FeNO level, baseline ICS dose level, visit, treatment by-visit interaction, baseline % predicted FEV1 value and baseline-by-visit interaction as covariates. The LS mean of each group, difference of LS means between treatment and placebo arms, 95% confidence interval and P value will be reported. In patients with baseline blood eosinophils \geq 0.3 Giga/L, the analysis will remain same as above except that the covariate of baseline eosinophil level will be removed.

Estimand of clinical efficacy of dupilumab versus placebo with treatment adherence

To assess the treatment effect when the patients adhere to the study treatment as directed, on-treatment % predicted pre-BD FEV1 measurements will be analyzed using the similar MMRM model as for the key secondary endpoint analyses, using the same estimation algorithm. The model will include on-treatment change from baseline in % predicted pre-BD FEV1 values up to Visit 8 (Week 12) as response variables. A % predicted pre-BD FEV1 value is considered as on-treatment if it's measured before or on the last dose date + 14 days. The on-treatment analyses for the key secondary endpoint will be performed in the Type 2 inflammatory asthma phenotype and baseline blood eosinophils \geq 0.3 Giga/L populations. The same set of covariates as specified for the key secondary endpoint analyses in each of the Type 2 inflammatory asthma phenotype and baseline blood eosinophils \geq 0.3 Giga/L populations will be used in the MMRM model for the on-treatment analyses. Measurements obtained during off treatment period will be considered as missing.

Sensitivity analyses with different censoring methods for pre-BD FEV1 potentially confounded by systemic corticosteroid use

In addition, two sets of sensitivity analyses with different methods of handling % predicted pre-BD FEV1 measurements confounded by the systemic corticosteroid use will be performed:

- Censoring method 1: The % predicted pre-BD FEV₁ measurements collected from systemic corticosteroid start date to systemic corticosteroid end date + 14 days will be excluded in order to reduce the confounding effect of systemic corticosteroids
- Censoring method 2: All % predicted pre-BD FEV₁ measurements collected on and after first day of systemic corticosteroid use will be excluded

The above two censoring methods will be applied to the key secondary endpoint analyses and the on-treatment analysis for the key secondary endpoint.

Handling of missing data

If a patient misses scheduled % predicted pre-BD FEV1 measurement during the first 12-week treatment, or withdraws from the study before Visit 8 (Week 12), he/she will have missing % predicted pre-BD FEV1 data from these time points up to Week 12. Descriptive statistics of % predicted pre-BD FEV1 by visit up to Week 12 will be summarized for patients with some missing data and patients with complete data up to Week 12 separately. Number of patients with missing % predicted pre-BD FEV1, reasons and timing for missing % predicted pre-BD FEV1 will be summarized by treatment groups. In addition, the following sensitivity analyses will be conducted to assess the robustness of the conclusion drawn based on the main model for the key secondary endpoint analyses to the missing data:

- *Pattern mixture model-multiple imputation (PMM-MI)*

Missing % predicted pre-BD FEV1 values will be imputed multiple times with adjustment for covariates including treatment, region, ethnicity, baseline eosinophil level, baseline FeNO level, baseline ICS dose level, baseline % predicted FEV1 value and reason of treatment discontinuation. Each of the complete datasets will be analyzed using the ANCOVA model with change from baseline in % predicted pre-BD FEV1 at Week 12 as the response variable, treatment, baseline weight, region, ethnicity, baseline eosinophil level, baseline FeNO level, baseline ICS dose level, and baseline % predicted pre-BD FEV1 value as covariates. Then the SAS MIANALYZE procedure will be used to generate statistical inference by combining results using Rubin's formula.

- *Control based PMM-MI*

The analysis is similar as the standard PMM-MI described above, except that it assumes that after withdrawal from the study, patients from the dupilumab groups would exhibit the same future evolution of % predicted pre-BD FEV1 as patients on the placebo who were not exposed to dupilumab.

- *Tipping point analysis*

First, missing values will be imputed by PMM-MI as illustrated above. The imputed values in placebo group will then be shifted by adding a sequence of positive values and the imputed values in dupilumab group will be shifted by subtracting a sequence of positive values. For each combination of the shift parameters, each of the imputed and shifted datasets will be analyzed with the ANCOVA model and their results will be combined using Rubin's formula to generate statistical inference. LS mean difference between dupilumab and placebo in change from baseline in % predicted pre-BD FEV1 at Week 12 and the corresponding p-values will be provided for each combination of shift parameters.

The missing data sensitivity analyses for the key secondary endpoint analysis will be performed in the Type 2 inflammatory asthma phenotype and baseline blood eosinophils ≥ 0.3 Giga/L populations. When performing the sensitivity analyses in the population with Type 2 inflammatory asthma phenotype, the model will include treatment, baseline weight, region, ethnicity, baseline eosinophil level, baseline FeNO level, baseline ICS dose level, visit, treatment by-visit interaction, baseline % predicted FEV1 value and baseline-by-visit interaction as covariates. When performing the sensitivity analyses in the population with baseline blood eosinophils ≥ 0.3 Giga/L, the baseline eosinophil level will be removed from the model covariates.

More details of the imputation and analyses methods are included in [Appendix D](#).

Subgroup analysis

To assess the consistency of treatment effects across the subgroup levels, subgroup analyses will be conducted for the change from baseline in % predicted pre-BD FEV1 at Week 12 in the same set of subgroups as defined for the primary endpoint of annualized rate of severe exacerbation events. The subgroup analyses (except for the baseline eosinophil levels and baseline FeNO levels) will be performed in the Type 2 inflammatory asthma phenotype population and baseline blood eosinophils ≥ 0.3 Giga/L population; and, the subgroup analyses for the baseline blood eosinophil level and baseline FeNO level will be performed in the full ITT population. The same MMRM model for the key secondary endpoint will be applied for the subgroup analyses.

When performing the subgroup analysis in the Type 2 inflammatory asthma phenotype population or the full ITT population, the model will include change from baseline in % predicted FEV1 values up to Week 12 as response variables, and treatment, baseline weight, region, ethnicity, baseline eosinophil level, baseline FeNO level, baseline ICS dose level, visit, treatment by-visit interaction, baseline % predicted FEV1 value and baseline-by-visit interaction as covariates. When performing the subgroup analysis in the baseline blood eosinophils ≥ 0.3 Giga/L population, the baseline eosinophil level will be removed from the model covariates. Furthermore, in the Type 2 inflammatory asthma phenotype, baseline blood eosinophils ≥ 0.3 Giga/L, or full ITT population, when performing the subgroup analysis that is defined by age, baseline weight, region, gender, baseline blood eosinophil level, baseline FeNO level, baseline ICS dose level, or baseline % predicted FEV1, the covariate that defines the subgroup will be removed from the model covariates.

Treatment-by-subgroup interaction at Week 12 and its p-value will be derived from an MMRM model. If quantitative treatment by subgroup interaction at Week 12 is detected with nominal p-value <0.05 for any subgroup factor, the Gail-Simon test will be used to test the qualitative interaction. Summary statistics of change from baseline in % predicted pre-bronchodilator FEV1 will be provided within each subgroup. Forest plot of LS mean difference and corresponding CIs comparing dupilumab vs placebo for the subgroups will be provided.

Distribution of change from baseline in percent predicted pre-BD FEV1

Water fall plots of change from baseline in % predicted FEV1 at Week 12 and Week 52 will be presented in the Type 2 inflammatory asthma phenotype population and baseline blood eosinophils ≥ 0.3 Giga/L population.

Treatment-by-Type 2 biomarker interaction

To examine the ability of FeNO to predict the treatment effect of dupilumab independent of blood eosinophil levels for the key secondary endpoint, the treatment-by-biomarker interactions will be tested with MMRM model, which includes change from baseline in % predicted FEV1 values up to Week 12 as response variables, and with the following different sets of model covariates, respectively. A threshold value of 0.15 will be utilized for the nominal p value of interaction test.

Biomarker covariate and treatment -by-biomarker interaction	Model covariates
Baseline biomarker as categorical variable:	
Baseline FeNO group (<20 ppb, ≥ 20 ppb), and treatment-by-baseline FeNO group interaction	MMRM with the treatment arm, baseline weight (≤ 30 kg, >30 kg), region, ethnicity, baseline FeNO level (<20 ppb, ≥ 20 ppb), baseline ICS dose level (medium/high), visit, treatment by-visit interaction, baseline % predicted FEV1 value and baseline % predicted FEV1 value -by-visit interaction, and treatment-by-baseline FeNO group interaction as covariates.
Baseline eosinophil group (<0.15 Giga/L, ≥ 0.15 Giga/L), and treatment-by- baseline eosinophil group interaction	MMRM with the treatment arm, baseline weight (≤ 30 kg, >30 kg), region, ethnicity, baseline eosinophil level (<0.15 Giga/L, ≥ 0.15 Giga/L), baseline ICS dose level (medium/high), visit, treatment by-visit interaction, baseline % predicted FEV1 value and baseline % predicted FEV1 value -by-visit interaction, and treatment-by- baseline eosinophil group interaction as covariates.
Baseline FeNO group (<20 ppb, ≥ 20 ppb), baseline eosinophil group (<0.15 Giga/L, ≥ 0.15 Giga/L), and treatment-by-baseline FeNO group interaction	MMRM with the treatment arm, baseline weight (≤ 30 kg, >30 kg), region, ethnicity, baseline eosinophil level (<0.15 Giga/L, ≥ 0.15 Giga/L), baseline FeNO level (<20 ppb, ≥ 20 ppb), baseline ICS dose level (medium/high), visit, treatment by-visit interaction, baseline % predicted FEV1 value and baseline % predicted FEV1 value -by-visit interaction, and treatment-by-baseline FeNO group interaction as covariates.
Baseline FeNO group (<20 ppb, ≥ 20 ppb), baseline eosinophil group (<0.15 Giga/L, ≥ 0.15 Giga/L), treatment-by-baseline FeNO group interaction, and treatment-by- baseline eosinophil group interaction	MMRM with the treatment arm, baseline weight (≤ 30 kg, >30 kg), region, ethnicity, baseline eosinophil level (<0.15 Giga/L, ≥ 0.15 Giga/L), baseline FeNO level (<20 ppb, ≥ 20 ppb), baseline ICS dose level (medium/high), visit, treatment by-visit interaction, baseline % predicted FEV1 value and baseline % predicted FEV1 value -by-visit interaction, and treatment-by- baseline eosinophil group interaction, and treatment-by-baseline FeNO group interaction as covariates.

Baseline biomarker as continuous variable:	
Baseline FeNO value, and treatment-by-baseline FeNO value interaction	MMRM with the treatment arm, baseline weight (≤ 30 kg, >30 kg), region, ethnicity, baseline FeNO value, baseline ICS dose level (medium/high), visit, treatment by-visit interaction, baseline % predicted FEV1 value and baseline % predicted FEV1 value -by-visit interaction, and treatment-by-baseline FeNO value interaction as covariates.
Baseline eosinophil value, and treatment-by- baseline eosinophil value interaction	MMRM with the treatment arm, baseline weight (≤ 30 kg, >30 kg), region, ethnicity, baseline eosinophil value, baseline ICS dose level (medium/high), visit, treatment by-visit interaction, baseline % predicted FEV1 value and baseline % predicted FEV1 value -by-visit interaction, and treatment-by- baseline eosinophil value interaction as covariates.
Baseline FeNO value, baseline eosinophil value, and treatment-by-baseline FeNO value interaction	MMRM with the treatment arm, baseline weight (≤ 30 kg, >30 kg), region, ethnicity, baseline ICS dose level (medium/high), visit, treatment by-visit interaction, baseline % predicted FEV1 value and baseline % predicted FEV1 value -by-visit interaction, baseline eosinophil value, baseline FeNO value, and treatment-by-baseline FeNO value interaction as covariates.
Baseline FeNO value, baseline eosinophil value, treatment-by-baseline FeNO value interaction, and treatment-by- baseline eosinophil value interaction	MMRM with the treatment arm, baseline weight (≤ 30 kg, >30 kg), region, ethnicity, baseline ICS dose level (medium/high), visit, treatment by-visit interaction, baseline % predicted FEV1 value and baseline % predicted FEV1 value -by-visit interaction, baseline eosinophil value, baseline FeNO value, treatment-by- baseline eosinophil value interaction, and treatment-by-baseline FeNO value interaction as covariates.

Slope analysis of post-bronchodilator % predicted FEV1

For post-bronchodilator % predicted FEV1, the rate of change in post-bronchodilator % predicted FEV1% (termed as % predicted FEV1 slope) will be compared between dupilumab and placebo in the Type 2 inflammatory asthma phenotype population and baseline blood eosinophils ≥ 0.3 Giga/L population. Change from baseline in post-bronchodilator % predicted FEV1 after Week 4 and after Week 8 will be analyzed correspondingly using linear mixed-effects model with treatment, baseline weight, region, ethnicity, baseline eosinophil level, baseline FeNO level, baseline ICS dose level, time since randomization, and treatment-by-time interaction, baseline post-bronchodilator % predicted FEV1 value as covariates in the Type 2 inflammatory asthma phenotype population; when performing the slope analysis in the baseline blood eosinophils ≥ 0.3 Giga/L population, the baseline eosinophil level will be removed from the model covariates Intercept and time since randomization will be treated as random effects in this mixed-effects model.

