11.4.2.1.1 Sensitivity Analysis

A supportive analysis to assess the treatment effect of dupilumab if patients adhere to the treatment and background asthma medication as directed is also provided. In this approach, the severe exacerbation events reported after the premature treatment discontinuation will be excluded from the analysis. Any measurement obtained after the first permanent stepping-up of background asthma medication will also be excluded from the analysis. The supportive analysis will be performed in the type 2 inflammatory phenotype and baseline blood eosinophils ≥ 300 cells/ μL populations and will use a negative binomial model with the same set of covariates as specified for the primary analysis in the two populations. This model will include severe exacerbation events occurring during the treatment epoch before any permanent stepping-up of background

asthma medication as the response variable and the log transformed duration of the treatment or from randomization to first permanent stepping-up of background asthma medication whichever is shorter will be the offset variable.

If patients withdraw from the study before Week 52 with severe exacerbation events that may occur after study discontinuation will not be observed, these patients are considered as patients with missing data on severe exacerbation. Number, reasons and timing of the missing data will be summarized by treatment groups. In the primary analysis, all observed data will be used regardless of treatment adherence or increase of asthma background medication. No imputation will be conducted for the missing severe exacerbation information after a patient prematurely withdraws from the study up to Week 52. In addition, sensitivity analyses based on pattern mixture model, placebo based pattern mixture model and tipping point analysis based on the same negative binomial model as being used in the primary analysis may be conducted to assess the robustness of the conclusion of the main model. Details of these sensitivity analyses will be described in the SAP.

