11.4.2.2.5 Sensitivity Analyses

Sensitivity analyses will only be conducted for the key secondary endpoint of change from baseline in pre-bronchodilator % predicted FEV1 at Week 12. A supportive analysis will be provided by applying the same model for the primary analysis with only on-treatment measurements obtained before any permanent stepping-up of the asthma background medication.

A sensitivity analysis based on LOCF will also be provided to assess the robustness of the conclusion from the primary analysis on change from baseline in pre-bronchodilator % predicted FEV1 at Week 12 against missing data. Details of the sensitivity analyses will be further provided in the SAP.

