An analysis to assess the efficacy of dupilumab if patients adhere to the treatment as directed is also specified. In this approach, the severe exacerbation events reported after the premature treatment discontinuation will be excluded from the analysis. Any exacerbation obtained after the first permanent stepping-up of background asthma medication (following at least two severe exacerbation per protocol) will also be excluded from the analysis. The supportive analysis for the primary endpoint will be performed in the Type 2 inflammatory asthma phenotype and baseline blood eosinophils ≥ 0.3 Giga/L populations. A negative binomial model with the same set of covariates as specified for the primary endpoint analysis in each of the Type 2 inflammatory asthma phenotype and baseline blood eosinophils ≥ 0.3 Giga/L populations will be used. This model will include severe exacerbation events occurring during the treatment epoch before any permanent treatment regimen change (including permanent IMP discontinuation and/or step-up of controller medication) as the response variable and the log transformed duration of the treatment epoch or from randomization to first permanent treatment regimen change whichever is shorter will be the offset variable. This approach defines the estimand to be the efficacy of dupilumab with treatment adherence.

Handling of missing data

If patients withdraw from the study before Visit 28 (Week 52), severe exacerbation events that may occur after study discontinuation will not be observed. These patients are considered as patients with missing data for the severe exacerbation endpoint. Number of patients with missing data, reasons and timing for patient withdrawals will be summarized by treatment groups. Summary statistics of selected demographic and baseline disease characteristics will be provided for patients with missing data and patients with complete data separately. Graphical summaries of the dropout patterns such as Kaplan-Meier plots of time to study discontinuation with different reasons of discontinuation may be provided to examine if there is any different missing pattern between treatment groups. In addition, the following sensitivity analyses will be conducted to assess the robustness of the conclusion drawn based on the main model for the primary analysis to the missing data:

- *Pattern mixture model (PMM-MI with logistic regression model)*

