For the efficacy assessment, the reference date for the derivation of relative days of events or findings will be the randomization day. If a patient receives IMP prior to the randomization by mistake, the reference date of efficacy assessment will be the date of the first IMP administration for that patient. For the primary analyses, all available values of scheduled measurements will be assigned to the appropriate visit window according to [Table 13](#). In the event of multiple measurements of the same test in the same window, the one closest to the targeted visit date will be used for the by-visit summary. If they are at the same distance to the target day, the latest one will be used. For the on-treatment sensitivity analyses, only scheduled measurements collected during the treatment epoch will be assigned to a time window.

Table 13 - Time window for efficacy variables

Visit	Target Day	Time windows for			
		Pre-bronchodilator Spirometry, ACQ-IA	Post-bronchodilator spirometry	PAQLQ(S)-IA, PACQLQ(S)-IA, PRQLQ-IA	EQ-5D-Y
Visit 1 (Week -4±1)	-28±7	<-14			
Visit 2 (Week 0)	1	-14-1-	1-	1-	1-
Visit 3 (Week 2)	15	1+-21	1+-21		
Visit 4 (Week 4)	29	22-35	22-42		
Visit 5 (Week 6)	43	36-49			
Visit 6 (Week 8)	57	50-63	43-70		
Visit 7 (Week 10)	71	64-77			
Visit 8 (Week 12)	85	78-98	71-126	1+-126	
Visit 10 (Week 16)	113	99-126			
Visit 12 (Week 20)	141	127-154			
Visit 14 (Week 24)	169	155-182	127-210	127-210	1+-266
Visit 16 (Week 28)	197	183-210			
Visit 18 (Week 32)	225	211-238			
Visit 20 (Week 36)	253	239-266	211-308	211-308	
Visit 22 (Week 40)	281	267-294			
Visit 24 (Week 44)	309	295-322			
Visit 26 (Week 48)	337	323-350			
Visit 28 (Week 52)	365	351-378(spirometry) 351-406(ACQ-IA)	309-406	309-406	267-406
Visit 29 (Week 56)	393	379-406(spirometry only)			
Visit 30 (Week 60)	421	407-434(spirometry only)			
Visit 31 (Week 64)	449	>434(spirometry) >406(ACQ-IA)	>406	>406	>406

1-: up to randomization and before 1st dose date/time; 1+-: after randomization or 1st dose date/time

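### The SAP's treatment-adherence analysis of Week 12 % predicted FEV1 omits the protocol's restriction to values before a permanent background step-up, and does not list the change

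*SAP*

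**What the plan says.** **FEV1, protocol.** Protocol 11.4.2.2.5 repeats the key secondary model "with only on-treatment measurements obtained before any permanent stepping-up of the asthma background medication". That is two conditions: on study drug, and before a step-up.

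**FEV1, SAP.** Under its treatment-adherence heading, SAP 2.4.4.2.1 states one condition: "A % predicted pre-BD FEV1 value is considered as on-treatment if it's measured before or on the last dose date + 14 days". It then says what is set aside: "Measurements obtained during off treatment period will be considered as missing". SAP 2.5.4 is consistent with this and adds no further cut: "For the on-treatment sensitivity analyses, only scheduled measurements collected during the treatment epoch will be assigned to a time window".

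**Exacerbations, protocol.** Protocol 11.4.2.1.1: "Any measurement obtained after the first permanent stepping-up of background asthma medication will also be excluded from the analysis".

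**Exacerbations, SAP.** SAP 2.4.4.1 uses the same treatment-adherence heading and keeps the step-up exclusion, with a qualifier that the protocol lacks: "Any exacerbation obtained after the first permanent stepping-up of background asthma medication (following at least two severe exacerbation per protocol) will also be excluded". The model sentence that follows counts events "before any permanent treatment regimen change (including permanent IMP discontinuation and/or step-up of controller medication) as the response variable", and the exposure is the treatment epoch or the time "from randomization to first permanent treatment regimen change whichever is shorter will be the offset variable".

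**Change log.** SAP Table 3, which records departures from the protocol's planned analysis, has one FEV1 entry: removal of age, sex and baseline height as covariates. SAP Table 2 mentions an elaboration of the estimand, described as a clarification. Neither table mentions step-ups.

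**The concern.** An adherence analysis is meant to show the effect when children take study drug and background therapy as directed. A child whose controller therapy is permanently raised while still on study drug no longer fits that description. The protocol removes that child's later FEV1 values; the SAP retains them.

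Step-up follows poor control, so it should be more common on placebo. Added controller therapy could then lift placebo FEV1 and reduce the estimated difference. That direction is plausible, but the documents do not establish it.

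There is also a problem of definition. SAP 2.4.4.1 and 2.4.4.2.1 use the same estimand name, yet one stops at a step-up and the other does not. A reader of the study report would reasonably assume a single rule. Because the change is not logged, neither the reader nor the programmer can tell whether it was intended.

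**Working it through.** The plan states no figure for this point. The check is a comparison of the rules, followed by an illustration of size.

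**1. Rules compared**

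| Analysis | Study-drug cut | Step-up cut |
|---|---|---|
| FEV1, Protocol 11.4.2.2.5 | yes | yes, any permanent step-up |
| FEV1, SAP 2.4.4.2.1 and 2.5.4 | yes, last dose + 14 days | none |
| Exacerbations, Protocol 11.4.2.1.1 | yes | yes, first permanent step-up |
| Exacerbations, SAP 2.4.4.1, model sentence | yes | yes, any permanent step-up, for both count and offset |
| Exacerbations, SAP 2.4.4.1, exclusion sentence | yes | yes, with a per-protocol parenthesis |

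Only the second row lacks the cut.

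**2. How many children could qualify for a per-protocol step-up by Week 12**

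Inputs:
- Step-up is permitted after two or more severe exacerbations (Protocol 8.2.1).
- Event start dates must be at least 28 days apart (SAP 2.1.3.1).
- Randomised numbers are 268 dupilumab and 134 placebo (Protocol 11.1).
- Rates of 1.0 and 0.5 per year and dispersion k = 1.5 come from the superseded design (Protocol Appendix O, SAP Table 1). They are assumptions here.

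Ignoring the 28-day rule, with mean m = rate × 12/52:

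P(≥2) = 1 − (1 + km)^(−1/k) − m(1 + km)^(−1/k − 1)

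- Placebo: m = 0.231, km = 0.346, so P = 1 − 0.820 − 0.141 = 3.9%.
- Dupilumab: m = 0.115, km = 0.173, so P = 1 − 0.899 − 0.088 = 1.3% (1.25% before rounding the terms).

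These are upper bounds. Simulating the same gamma-Poisson process with the 28-day gap (100,000 children per setting) gives:

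| | Placebo | Dupilumab |
|---|---|---|
| k = 1.5 | 2.1% | 0.6% |
| k = 0.5 to 2.5 | 1.5% to 2.5% | 0.4% to 0.8% |

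In all randomised children, 134 × 0.0209 ≈ 3 and 268 × 0.0058 ≈ 2. The analysis is run only in the Type 2 and eosinophils ≥0.3 Giga/L populations (about 345 and 255 children, SAP 1.1). At 2:1 these hold 115 and 85 placebo children, giving 115 × 0.0209 = 2.4 and 85 × 0.0209 = 1.8. The dupilumab counts are 230 × 0.0058 = 1.3 and 170 × 0.0058 = 1.0.

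**3. Rough shift in the FEV1 difference**

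Suppose every eligible child is stepped up and gains g points of % predicted FEV1 by Week 12. The shift toward no difference is about (0.0209 − 0.0058) × g = 0.0151g. The documents give no g. For assumed values of 2, 5 and 10 points, the shift is 0.03, 0.08 and 0.15 points. With the upper-bound probabilities (0.0392 − 0.0125 = 0.0267) it is 0.05, 0.13 and 0.27 points.

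**4. Does another analysis already cover it?**

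SAP 2.4.4.2.1 also applies two systemic-corticosteroid censoring methods to the on-treatment analysis. Every severe exacerbation involves systemic corticosteroids by definition, so method 2, which drops all values from first use onward, removes everything after a per-protocol step-up. Method 1 readmits values once 14 days have passed after the steroid course. The main on-treatment analysis applies neither.

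**The case against.** **The effect is negligible.** Very few children can qualify by Week 12, step-up is then optional, and the analysis is supportive and absent from SAP Tables 9 and 10. If the bias runs toward no difference, it is conservative. This stands as an argument about size. It does not explain why the SAP departs from the protocol.

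**Censoring method 2 deals with it.** This is true for per-protocol step-ups in that one version. But method 2 also discards values after any steroid course, so it answers a different question. It also misses step-ups that no steroid course preceded.

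**The SAP was entitled to change it.** The protocol leaves details to the SAP, SAP 1.6 promises only major changes, and the FEV1 text speaks of adherence to study treatment alone. A deliberate narrowing is possible. Removing one of two stated conditions is more than adding detail, however, and if it was intended it needs an entry and a reason.

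**A stronger reading of the exacerbation analysis.** From the parenthesis in "Any exacerbation obtained after the first permanent stepping-up of background asthma medication (following at least two severe exacerbation per protocol) will also be excluded", a reader might infer that events after an off-protocol step-up are kept. The documents do not support that. The model sentence ends both count and offset at any permanent regimen change and names controller step-up without a qualifier. The parenthesis can also be read as describing when the protocol permits a step-up. It is an inconsistency of wording, although SAP 2.4.2 also summarises step-ups made according to protocol, so a programmer could derive the wrong date from it.

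**Conclusion.** The discrepancy is real and confined to one analysis. SAP 2.4.4.2.1 keeps FEV1 values that Protocol 11.4.2.2.5 excludes, and the SAP does not record the change. It should be corrected because the correction is cheap and makes the analysis match its estimand, not because a result is likely to change.

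The size rests on superseded rates and on step-ups occurring only as the protocol allows: about 2.1% versus 0.6% of children eligible by Week 12, and a shift of about 0.15 points or less on the gap-adjusted figures if the gain is at most 10 points. Off-protocol step-ups would add to this; the documents give no number for them.

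A reader might also cite the 52-week figures as evidence of a large problem. The same simulation puts about 23% of placebo and 10% of dupilumab children at two or more events by Week 52. Those figures belong to the exacerbation analysis, which already has the cut, and say nothing about Week 12 FEV1. No primary or key secondary test is affected.

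**What to change.** 1. In SAP 2.4.4.2.1, add to the on-treatment definition: *and before any permanent step-up of background asthma medication*. Make the matching addition in SAP 2.5.4 for this analysis. If the omission was deliberate, enter it in Table 3 with a reason instead.
2. State how the step-up date is derived. Take it from the prescribed asthma controller medications eCRF page (SAP 2.4.2.1), because the summary in SAP 2.4.2 covers only step-ups made according to protocol. State that the temporary ICS increases allowed by Protocol 8.2.1 do not count as permanent step-ups.
3. In SAP 2.4.4.1, delete the parenthesis from the exclusion sentence so that it agrees with the model sentence and with Protocol 11.4.2.1.1. The model itself needs no change.

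The cost is a few SAP sentences and one derived date. No new data collection is needed, provided that the eCRF page lets a permanent change be told apart from a temporary one; that should be confirmed before unblinding. The change concerns which data enter an analysis and has no bearing on how children are treated.
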